The study PI and co-investigators will be responsible for the evaluation, monitoring, and documentation of events meeting the criteria and definition of an adverse event (AE) or serious adverse event (SAE) as provided in this clinical investigation. The study participants will be evaluated for any possible AEs from the time written study informed consent is obtained until study closure or the subject exits the study.

 Any pre-existing condition unless a worsening of that condition in terms of nature, severity, or frequency develops.

Version 2014JAN31 Confidential Page 8 of 13

- Medical or surgical procedure unrelated to the clinical protocol (i.e., dental or cosmetic procedure)
- Technical observation or a device events that does not result in a medically undesirable situation for the subject

Documentation of Adverse Events

All AEs from the time the study informed consent is signed through the final study visit will be recorded as AEs on the study event log; each event being documented separately. All AEs and SAEs will be followed until:

- AE is resolved and has returned to normal/baseline or has stabilized
- Subject has withdrawn from the study
- AE is judged by the investigator to be no longer clinically significant
- Study closure at which time, the responsibility for following any ongoing AEs will be transferred to the incoming clinical care team.

[name] will serve as Point of Contact to which the team will report adverse events. All non-serious adverse events will be reported to the Ohio State University Institutional Review Board (IRB) during the annual reporting period.

For those events that are determined to be related to stimulation therapy or device specific, the sponsor/investigator will report the strength of the relatedness using the following terms:

- **Definitely related:** The event is resolved by discontinuing stimulation
- **Probably related:** The event resolves upon discontinuing stimulation and cannot be reasonably explained by the subject's current clinical state
- **Possibly related:** The event may have been produced by the study subject's clinical state, however, the effect of stimulation cannot be ruled out
- **Unlikely related:** The event did not occur temporally to stimulation and can be explained by the subject's current clinical state or any other cause
- **Unrelated:** The event is explained by the subject's current clinical state or any other cause

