For purposes of determination of a UADE the following categories will be considered related: "definitely related" and "probably related".

Reporting of Serious Adverse Events

SAEs reported during the protocol defined reporting period per section 4.1.4 will be:

- Evaluated for their relatedness per section 4.1.4
- Reported to the Data Safety Monitoring Committee

Procedures for Minimizing Risks

The risks associates with this study are minimal. Participants may terminate from the study if they wish at any time. Study participants may also wish to discontinue participation for any reason. Subjects who prematurely withdraw from the study due to an adverse event will be followed (e.g. telephone contact, and/or follow-up visits, etc.) until resolution of the event. Risks to confidentiality are negligible in this protocol, since participants will not be identified by name, or by any personal data, in any summary reports or publications. CRFs will be maintained in locked files and password-protected databases behind the Ohio State University Medical Center firewall. Data and safety monitoring activities for this study will continue until all subjects have completed their participation in the study.

Potential Benefits

Functional electrical stimulation (FES) systems have been created that stimulates muscle and restores functional movement in paralyzed limbs. This is one of the first studies in humans to combine high definition neuromuscular stimulation and EEG to produce real-time control of a paralyzed limb.

Study Justification

The target population will be people with C4-6 ASIA A spinal cord injuries (motor and sensory complete neurologic injuries) who are more than 1 year post injury and who are neurologically stable. This population is more likely to have reached a stable level of functional movement. People with this level of paralysis are totally dependent in all aspects of self-care. Restoration of functional movement in this population requires exploration of neuroprosthetic applications to increase functional movement that has quality of life implications. This BCI system is the first

Version 2014JAN31 Confidential Page 10 of 13

attempt to utilize cortical sensors and a high definition stimulation system to bypass the injured spinal cord and produce volitional movement in humans.

Device Description

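### The top relatedness grade asks for less evidence than the grade below it, and one event can fit grades on both sides of the UADE relatedness line with no stated tie-break

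*Combined protocol and SAP*

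**What the plan says.** The relatedness terms are in the section Documentation of Adverse Events:

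- The top grade, *Definitely related*, has a single condition: "The event is resolved by discontinuing stimulation".
- For *Probably related*, the second grade, the test has two parts: "The event resolves upon discontinuing stimulation and cannot be reasonably explained by the subject's current clinical state".
- The middle grade, *Possibly related*, is worded this way: "The event may have been produced by the study subject's clinical state, however, the effect of stimulation cannot be ruled out".
- For *Unlikely related*, the plan asks for two things: "The event did not occur temporally to stimulation and can be explained by the subject's current clinical state or any other cause".
- The lowest grade, *Unrelated*, is given by one clause: "The event is explained by the subject's current clinical state or any other cause".

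The lead-in applies the scale to a subset of events: "For those events that are determined to be related to stimulation therapy or device specific". After the list comes the UADE rule. It says that "the following categories will be considered related" and names only *Definitely* and *Probably*. *Possibly*, *Unlikely* and *Unrelated* therefore do not count.

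The next section, Reporting of Serious Adverse Events, has SAEs evaluated for relatedness by reference to a section 4.1.4, a number that the public text does not show. That text has no precedence rule, no statement that the grades are mutually exclusive, and no adjudication step for an event that fits more than one grade.

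**The concern.** A causality scale is useful only if each step up requires more evidence and each event has one place on it. Here the top step drops a condition that the second step imposes. An event with a good alternative explanation fails *Probably* but still qualifies for *Definitely*.

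Two things are at stake. First, the reported strength of relatedness has no dependable order at its upper end, so a count of *Definitely related* events cannot be read as the count with the best evidence against the device. Second, the UADE rule draws its line between *Probably* and *Possibly*, and one event can satisfy definitions on both sides of that line. Two investigators with the same facts could then classify it differently for UADE purposes, and both would be following the protocol.

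**Working it through.** The plan gives no figure to reproduce. The check compares the definitions as logical conditions.

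**Conditions taken from the five definitions**
- R: the event resolves when stimulation is discontinued.
- T: it is temporal to stimulation.
- C: the clinical state can explain it.
- O: another cause can explain it.
- E: it *is* explained by the clinical state or another cause.
- X: an effect of stimulation cannot be ruled out.

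**Definitions in these terms**
- Definitely = R
- Probably = R and not C
- Possibly = C and X
- Unlikely = not T, and (C or O)
- Unrelated = E

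**Three readings of E**
- (a) E means the same as (C or O).
- (b) E is firmer: it implies (C or O) but is not implied by it.
- (c) As (b), and E also means that stimulation is ruled out (E excludes X).

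**Number of consistent profiles**
- (a) R, T and X are free and there are 4 combinations of C and O: 2×2×2×4 = 32.
- (b) Each of the 3 combinations with C or O allows two values of E, and the remaining one allows one: 8×(3×2+1) = 56.
- (c) Each of those 3 combinations allows 3 pairs of E and X, and the remaining one allows 2: 2×2×(3×3+2) = 44.

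**Results**

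| Check | (a) of 32 | (b) of 56 | (c) of 44 |
|---|---|---|---|
| Meets *Definitely* | 16 | 28 | 22 |
| Meets *Probably* | 8 | 12 | 10 |
| *Probably* but not *Definitely* | 0 | 0 | 0 |
| *Definitely* but not *Probably* | 8 | 16 | 12 |
| Both *Definitely* and *Possibly* | 4 | 8 | 4 |
| Both *Definitely* and *Unrelated* | 12 | 12 | 6 |

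The *Definitely*/*Possibly* row can be checked by hand. It needs R, C and X. Then T and O are free, which gives 4 under (a). E is free as well under (b), which gives 8. E must be absent under (c), which gives 4.

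**What follows**
1. *Probably* lies strictly inside *Definitely* under every reading. This needs only the two definitions: one is R, the other is R with a further condition.
2. The events in *Definitely* but outside *Probably* are those that resolve on stopping and have a clinical-state explanation. If stimulation is also not ruled out, they meet *Possibly* by its own words. One label is related for a UADE and the other is not.
3. *Unrelated* has no condition on timing or on response to stopping. An event that resolves on stopping can therefore meet it too, unless being explained is taken to mean a sole cause.

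The counts show that the overlaps exist. They are not probabilities, since profiles are not equally likely and some would be rare in practice.

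**The case against.** **The wording may carry a causal meaning.** *Resolved by* can be read as stronger than *resolves upon*, which would give *Definitely* something that *Probably* lacks. The definitions do not say so, and the investigator observes the same thing in both cases. Even on that reading, *Definitely* excludes no alternative cause.

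**The inversion alone may move nothing.** Both upper grades count as related, so an event that meets both is unaffected. That is right, but the events that matter are those that meet *Definitely* and fail *Probably*. They reach the related side only because the top grade omits the condition.

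**The lead-in may make *Unrelated* moot.** It restricts the scale to events already judged related or device specific. The scale still lists *Unrelated*, and the conflict between *Definitely* and *Possibly* does not depend on it.

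**A rule may stand elsewhere.** The cited section 4.1.4 cannot be identified, so the finding is limited to the public text.

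**Capture does not depend on the grade.** All AEs are logged, and SAEs go to the Data Safety Monitoring Committee with no stated relatedness threshold. This stands: the fault concerns classification, not missed events.

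A reader might also infer three stronger points that the documents do not support:
- *That the bottom of the scale is inverted in the same way.* *Unlikely* says the event can be explained and *Unrelated* says it is explained, which may be the firmer statement. Under readings (b) and (c), neither grade contains the other.
- *That every event which resolves and has another possible explanation is both *Definitely* and *Unrelated*.* That holds only if *can be* and *is* mean the same.
- *That the whole UADE decision, for example for autonomic dysreflexia, depends on the label.* Only the relatedness element of the UADE determination appears in the text, and Risks already foresees dysreflexia.

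**Conclusion.** The concern holds for the upper end of the scale and for the overlap across the UADE line. The top grade requires strictly less than the one below it. An event that resolves on stopping, may be due to the clinical state, and for which stimulation is not ruled out fits *Definitely* and *Possibly* under all three readings. It can also fit *Unrelated* if being explained is not read as a sole cause.

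The consequence is limited to the relatedness element of the UADE determination and to the reported strength of relatedness. The number of participants affected cannot be estimated, because the documents give no event rates.

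The conclusion assumes that the definitions mean what they literally say and that no precedence rule exists outside the public text. The change should be made: this is a stated rule that misorders events, not a missing detail.

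**What to change.** Reword the scale and reconcile it with the UADE rule:

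- ***Definitely related*** should require at least everything that *Probably related* requires, including that there is no reasonable alternative explanation. That should cover other causes as well as the clinical state, since *Probably* now mentions only the latter.
- ***Unrelated*** should require that an effect of stimulation is ruled out. It should not be barred for every event that occurs during a session, because a coincidental event with a proven other cause must still be gradable as *Unrelated*.
- **Exclusivity:** define the five grades so that each event belongs to one.
- **Tie-break:** where two grades still fit, record the more related one.

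The first two changes remove the overlaps at issue. *Definitely* would then need no alternative explanation, whereas *Possibly* needs a possible clinical-state cause and *Unrelated* needs an explanation, so no event could meet *Definitely* together with either. *Possibly* (stimulation not ruled out) and *Unrelated* (ruled out) would also be disjoint.

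The cost is protocol wording and the key to the event log, with no added visits, measurements or participants. Some events would change grade. Some now open to *Unrelated* would be recorded as at least possibly related. Some that clear on stopping but have a reasonable other explanation would move from *Definitely* to *Possibly*, which the UADE rule does not count. The sponsor should confirm that the UADE rule, read with the new definitions, captures the events it is meant to capture.

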submission is to demonstrate high definition neuromuscular stimulation of a paralyzed limb through computer-generated commands (or as triggered by a battery-operated EEG wireless headset). This will be an important step towards creating a neural bridge/bypass for patients with paralysis from spinal cord injury, stroke, or motor neuron disease. See Figure 1 for an overall system diagram and neuromuscular sleeve and glove components of the system.

The high definition Neuromuscular Stimulator is an investigational device developed by Battelle (Columbus, Ohio) that has been reviewed by a registered IRB (at Battelle) and has been used with human subjects with no adverse effects. The sleeve to be added in figure 1 (b,c) is a non-significant risk addition. The sleeve has been approved by the FDA in a significant risk study (see attached) that uses a chip implanted into the motor cortex. The sleeve itself is a non-significant risk device and does not elevate the present study to significant risk.

Version 2014JAN31 Confidential Page 3 of 13

[figure not shown]

Figure 1. a) Overall Neural Bridging System Diagram.; b,c) Neuromuscular stimulation sleeve and glove

Study Rationale

Most neuromuscular stimulation systems have large area pads and only allow gross motion. The high definition technology developed by Battelle will allow finer movements, including individual finger movement. The objective of this study is to demonstrate high definition non-invasive neuromuscular stimulation of an upper extremity in tetraplegic, also termed quadriplegic, participants as an important step towards developing a neural bridge/bypass for spinal cord injury or motor neuron disease and rehabilitation in stroke patients. In initial sessions, the computer will generate pre-determined movements and create the corresponding stimulation patterns and isolate individual wrist and hand/finger movements (after a calibration period).

In later sessions, and with training, the participant may be able to imagine a small number (1-3) basic movements that are detected by the EEG headset and then be evoked by the Neuromuscular Stimulator. The stimulation NMES will be in the form of a cuff/array is comprised of 12mm circular or a sleeve consisting of a flexible circuit that has electrodes with custom of 12mm diameter. In the case of the sleeve, the cuff and electrodes will be housed in a spandex-type material. A non-toxic conductive enhancer (hydrogel discs applied, or conductive

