lotion) lotion will form the interface between the electrodes and the skin allowing stimulation of small and large muscles and in the arm and hand to evoke a wide variety of spatial patterns and associated movements. The optional glove (Figure 1, b and c) connects to the sleeve and provides information back to the system about the position of the hand and arm in space, as well as the flexion and extension of the fingers and wrist. The glove does not provide stimulation and is for positional information gathering only.

Purpose

The purpose of this study is to demonstrate high definition non-invasive neuromuscular stimulation of an upper extremity in tetraplegic participants. This will be an important step towards developing a neural bridge/bypass for spinal cord injury or motor neuron disease and rehabilitation technology for stroke patients as well.

Protocol Overview and Design

The target population will be people with C4-6 ASIA A spinal cord injuries (motor and sensory complete neurologic injuries) who are more than 1 year post injury and who are neurologically stable.

Protocol Specifics

Participation Criteria

This study will plan to enroll up to 15 subjects who have been diagnosed with tetraplegia. Study participants will be persons of any race, ethnic group, or gender. Participants who enter will be free to withdraw from the study at any time without affecting their access to other treatments at OSU and affiliated hospitals. The first 5 eligible and consenting participants will be accepted into this study. No gender or minority will be excluded. However, since the sample size is small and participants will be accepted on a first come, first served basis, there may be inadequate representation of ethnicities, genders, and race in the study sample.

The total duration of the study is expected to be about 18 months, and each participant is expected to be on the study for about 6 months. Once the study is completed, participants will be discontinued from the study. Participants may also discontinue the study if they wish at any time.

Version 2014JAN31 Confidential Page 5 of 13

Inclusion and Exclusion Criteria

Inclusion Criteria:

- Must be 21 years or older.
- Must be tetraplegic (C4-6 ASIA A)
- 12 months post injury and neurologically stable
- Participant is willing to comply with all follow-up evaluations at the specified times.
- Participant is able to provide informed consent prior to enrollment in the study.

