Statistical analysis will be conducted with a biostatistician consultant. Continuous outcome variables will be summarized by the mean, median, standard deviation, minimum and maximum. Adverse effect data will be reported continuously, including all serious and non-serious adverse effects.

Primary and Secondary Outcomes

The primary outcome measure of this study is the achievement of individual wrist and hand/finger joint movement via high definition neuromuscular stimulation.

The targeted primary and secondary outcomes are therefore as follows:

- Primary outcome- consistent and repetitive voluntary movement in the targeted muscle groups
- Secondary outcome- consistent movement in the targeted muscle groups that is functional (manipulate or pick up an object)

Risk Analysis

Risks

Training and therapeutic sessions involving functional electrical stimulation will need to be monitored for autonomic dysreflexia signs and symptoms.

As with any muscle stimulator, there can be a risk of excessive current and skin irritation or burns. The Neuromuscular Stimulator, however, limits the average output current density to less than 2mA/cm² at the skin and the average power density to less than 0.25W/cm² to provide safe levels and avoid tissue damage However, despite these built-in safety limits, current and power density could exceed FDA guidelines if electrodes lift off of the skin. This has the potential to cause potentially causing minor irritation or first degree burns locally. The research investigator will monitor frequently during test sessions for any signs of electric shock, skin irritation, and/or burns. The sleeve material itself is spandex, with registration marks printed on it. The material itself has been tested for biocompatibility; the printing has not, nor has the sleeve after laundering. The investigators, who will already be monitoring frequently for signs of irritation from electric shock, will also monitor for signs of allergic skin reaction. The sleeve has been approved by the FDA in a significant risk study (see attached) that uses a chip implanted into the motor cortex. The sleeve itself is a non-significant risk device and does not elevate the present study to significant risk.

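### As the primary outcome bullet is worded, wrist movement a participant already had can count as success, because neither eligibility nor scoring requires the target movement to be absent at baseline

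*Combined protocol and SAP*

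**What the plan says.** **Eligibility.** The Inclusion Criteria state "Must be tetraplegic (C4-6 ASIA A"), at least 12 months after injury and neurologically stable. No inclusion or exclusion criterion refers to residual movement in the arm to be tested, and no rule says which arm that is.

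**Population.** Study Justification describes the C4-6 group without distinction by level: "People with this level of paralysis are totally dependent in all aspects of self-care". The sentence before it says "This population is more likely to have reached a stable level of functional movement".

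**Objective.** Previous Work states the aim as to "demonstrate high definition neuromuscular stimulation of a paralyzed limb through computer-generated commands", or as triggered by an EEG headset.

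**Primary outcome.** Primary and Secondary Outcomes words it twice. The opening sentence reads "The primary outcome measure of this study is the achievement of individual wrist and hand/finger joint movement via high definition neuromuscular stimulation". The bullet below it reads "consistent and repetitive voluntary movement in the targeted muscle groups". The targeted muscle groups are not named.

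**Baseline and analysis.** Phase I lists a physical and neurological exam, an EMG, and fitting and calibration of the stimulator. Outcomes and Data Analysis gives descriptive summaries of continuous variables. It provides no change from baseline, no comparison with stimulation off and no control group.

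**The concern.** The study sets out to show movement in a limb that cannot otherwise move. According to Device Description, the stimulator has already produced wrist and finger movement, and the related figure is captioned as an able-bodied study. What this trial adds is therefore the paralysis, and the claim needs the target movement to be absent without the device.

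The plan does not secure that for each movement. If a participant enters with some active wrist extension, and the wrist extensors are among the targeted muscle groups, repeated voluntary wrist extension meets the bullet's wording whether or not the system contributed. The EEG-triggered sessions add a practical route: a participant asked to imagine a movement might make it, and no scoring rule would separate that from a triggered one. In a small uncontrolled series, a reader could not tell retained wrist movement from restored movement.

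**Working it through.** The plan states no success rate, threshold or power, so there is no figure to reproduce. The check is mainly textual, followed by one illustration.

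**Step 1. Can someone with wrist movement enrol?** C6 is inside the eligible range. The documents do not say what a C6 level preserves. The criterion invokes the ASIA classification. If C6 is read there as the neurological (motor) level, the wrist extensors are the key muscles for that level and may keep some active movement; the A grade concerns completeness in the lowest sacral segments and does not remove it. This reading is an assumption, because the protocol does not say whether C4-6 is the motor level or the injured segment. On either reading, no criterion excludes a person with residual wrist movement in the tested arm.

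**Step 2. Can that movement be scored as success?**

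| Feature | Opening sentence | Bullet |
|---|---|---|
| Movement | individual wrist and hand/finger joints | targeted muscle groups, not named |
| Must be produced by stimulation | yes | not stated |
| Must be voluntary | not stated | yes |
| Must be absent at baseline | not stated | not stated |

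Unaided movement fails the opening sentence but can satisfy the bullet. The two wordings give different answers for the same participant.

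**Step 3. Does anything else separate the two?** The neurological exam and EMG would probably record residual function before testing. Neither is linked to eligibility, choice of target movement or scoring, and the analysis section makes no comparison that would do the work instead.

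**Step 4. How likely is it that the question arises?** The documents give no distribution of injury levels, so the C6 share q is assumed. With independent enrolment, P(at least one C6 participant) = 1 − (1 − q)^n. The protocol gives both 5 (first eligible participants accepted) and 15 (maximum), so both are shown.

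| q (assumed) | n = 5 | n = 15 |
|---|---|---|
| 20% | 1 − 0.8^5 = 67.2% | 1 − 0.8^15 = 96.5% |
| 1/3 | 1 − (2/3)^5 = 86.8% | 1 − (2/3)^15 = 99.8% |
| 40% | 1 − 0.6^5 = 92.2% | 1 − 0.6^15 = 99.95% |

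These are chances of enrolling a C6 participant. They are not chances that wrist extension is retained, or that it is miscounted.

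**The case against.** The strongest reply is that the opening sentence already requires movement through stimulation, and the bullets are introduced as following from it. Read together, unaided movement is not the outcome. The described procedures, pre-set computer patterns and EEG triggering, point the same way. This stands in part: it rules out saying that the primary outcome as a whole is already met at baseline. It does not close the gap, because the bullet drops the stimulation condition, adds the word voluntary, and is itself labelled the primary outcome.

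A second reply is that the documents never say C6 participants keep wrist extension. The General Introduction speaks of injury to a cervical segment, and the target population is glossed as motor and sensory complete. If C6 is the injured segment, preserved function there does not follow. This stands as a limit. A reader might infer that every C6 participant, or a typical one, arrives with wrist extension intact; the documents do not support that, and the point is confined to what may be retained.

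A reader might also infer a size: that each such participant moves the success rate by 20 points at n=5 (1/5) or 6.7 points at n=15 (1/15). That needs a per-participant success rate, which the plan does not define, and a participant who would otherwise have failed. Neither can be taken from the documents.

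Finally, the sentence on total dependence is background and governs no procedure. Rewording it, or reporting by motor level in so small a sample, would change little.

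**Conclusion.** The point holds in a limited form. Eligibility does not require the target muscles of the tested arm to be paralyzed, one of the two primary outcome wordings does not require stimulation to cause the movement, and no scoring rule uses the baseline findings. Retained wrist extension can therefore be counted as success under the bullet; the documents do not show that it will be. The exposure is mainly to wrist extension, not to finger movement.

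The C6 part rests on reading C6 as the neurological (motor) level, which the protocol leaves open. The probabilities rest on an assumed C6 share and say only that, at shares of 20% to 40%, at least one C6 participant is more likely than not even at n=5. The effect on the result itself cannot be estimated. The change should be made, because it affects what the main conclusion may claim and uses examinations already scheduled.

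**What to change.** Add a scoring rule to Primary and Secondary Outcomes and a matching entry to the Phase I form:

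- Before calibration, name the study arm and the target movements, and record from the Phase I exam which of them the participant can make unaided.
- Count toward the primary outcome only target movements that were absent at baseline and are produced with stimulation.
- Report target movements present at baseline separately.
- Reword the bullet to agree with the opening sentence, for example: repeated, consistent movement, produced with stimulation, in target movements that the participant could not make at baseline.

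The rule works whichever meaning of C6 was intended, and it excludes nobody on injury level. It adds protocol wording and a short baseline entry, with no extra visit. The downside is fewer countable wrist movements in some participants, so the success figure may be slightly less favourable.
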